Clinical Study Protocol

Protocol Name: A Clinical Study of Disitamab Vedotin for Injection Combined With Penpulimab Injection in Neoadjuvant Therapy for Patients With HER2-expressing Cisplatin-intolerant cT2-T4aNxM0 Bladder Urothelial Carcinoma

Sponsor: Sun Yat-sen Memorial Hospital, Sun Yat-sen University

Version number: V1.0

Version date: 2022.5.1

Signature confirmation of scheme:

Compliance Statement

In compliance with the Provisions of the Good Laboratory Practice Regulations, Administrative Measures for Investigator-initiated Clinical Studies in Medical and Health Institutions (for Trial Implementation) and the Declaration of Helsinki, participants pledged to conduct this study in accordance with this protocol. Participants must be trained to conduct the study after obtaining the written approval of the Ethics Committee and the informed consent of the subjects. Protocol modifications need to be re-approved.

I. programme summary

Project Name: A Clinical Study of Disitamab Vedotin for Injection Combined With Penpulimab Injection in Neoadjuvant Therapy for Patients With HER2-expressing Cisplatin-intolerant cT2-T4aNxM0 Bladder Urothelial Carcinoma

Abbreviation of Scheme: RC48-C039

Test purpose:
 
To evaluate the efficacy and safety of neoadjuvant treatment with Disitamab Vedotin for Injection Combined With Penpulimab Injection in patients with cT2-T4aNxM0 bladder urothelial carcinoma and HER2-expressing cisplatin intolerance.

Test brief:
 
The single-armed, exploratory clinical study of vidicon monoclonal antibody combined with pie Ampley monoclonal antibody designed for cisplatin-intolerant patients with cT2-T4aNxM0 bladder urothelial carcinoma in this study confirmed the effectiveness and safety of the new adjuvant treatment of vidicon monoclonal antibody combined with pie Ampley monoclonal antibody for cisplatin-intolerant patients with cT2-T4aNxM0 bladder urothelial carcinoma, and finally provided new evidence-based evidence for new adjuvant treatment of such patients.

Sample size:
 
This is a prospective clinical study. It is intended to collect 48 patients with cT2-T4aNxM0 bladder urothelial cancer who are HER2-expressing and cisplatin-intolerant, and all of them have received neoadjuvant treatment with vidicon monoclonal antibody in combination with pie Ampley monoclonal antibody.


research centre
 
Sun yat-sen university memorial hospital The Third Affiliated Hospital of Sun Yat-sen University Southern hospital of southern medical university Zhujiang hospital of southern medical university The Third Affiliated Hospital of Southern Medical University

Efficacy evaluation
 
Imaging evaluation by independent review experts according to the specific situation of patients, determine the evaluation time and evaluation method.

Data management and statistical analysis
 
SAS 9.4 statistical software was used for statistical analysis. Unless otherwise specified, all statistical tests will use a one-sided test with $\alpha=0.05$ and the confidence intervals will use a one-sided 95% confidence interval.

Estimated Start and End Time: Start Time: June 2022; End: April 2026

II. introduction

2.1 Research background

Bladder cancer is a common malignant tumor worldwide, and there are about 430,000 newly diagnosed patients every year [2]. According to the clinical TNM staging of bladder cancer, bladder cancer can be divided into non-muscular layer invasive bladder cancer (NMIBC) with high recurrence rate, muscular layer invasive bladder cancer (MIBC) with high metastasis risk, and metastatic bladder cancer (mBC) with high mortality. Treatment options for different stages of bladder cancer are different. NMIBC can be treated by transurethral resection of the bladder, combined with intravesical instillation of BCG. MIBC's preferred treatments were radical cystectomy and neoadjuvant platinum-based chemotherapy; Intravenous chemotherapy is an option for patients with mBC, but it is intolerable to approximately 50% of patients due to inhibitory adverse events due to chemotherapeutic agents and/or delayed treatment in non-responders.

In recent years, immune checkpoint inhibitors (ICIs) have become a new option for the treatment of bladder cancer. A study of 114 patients with MIBC(T2-4aN0M0) showed that a complete pathological response rate (CRR) of 37% was achieved with three courses of neoadjuvant immunotherapy with 200 mg Pembrolizumab before radical resection [3-4]. A one-arm second-stage clinical trial included 95 patients with MIBC who received two cycles of Atezolizumab before radical resection. About 31% of the patients experienced complete pathological reaction during radical resection. The pathological stage of more than half of the patients was reduced to NMIBC, and the one-year recurrence-free survival rate (RFS) was 79% [5]. The above studies have demonstrated that neoadjuvant immunotherapy based on ICIs is a therapeutic option for patients with MIBC, especially those who are intolerant to chemotherapy. Studies have confirmed that after tumor resection, neoadjuvant immunotherapy will continue to trigger a stronger immune response mainly by CD8+ T lymphocytes, leading to longer survival time for patients [6]. In addition, the surgical safety of radical resection after neoadjuvant immunotherapy is not significantly different from other methods [7]. Although ICIs can benefit more patients with MIBC than neoadjuvant chemotherapy, the use of ICIs still faces many challenges. First, there are currently no biomarkers that can predict the sensitivity of patients with MIBC to new ICIs-based adjuvant immunotherapy. The guidelines point out that PD- L1 expression and tumor mutation burden may predict the pathological response of ICIs treatment in some patients, but it is still not recommended as the basis of treatment selection [8]. Second, some patients lose the opportunity of radical surgery due to adverse events caused by ICIs treatment [9]. Finally, there is still controversy over whether ICIs alone or in combination with other immune and chemotherapy regimens is optimal.

A C014 study published on ASCO 2021 showed excellent anti-tumor activity with the combination of vidicon and tripril monoclonal antibody, with a therapeutic ORR of 94.1% in 17 evaluable patients. The ORR of the combination regimen was also 100% in 10 new patients. Further

analysis revealed that the combination regimen achieved excellent efficacy regardless of the expression status of HER2 and PD-L1 in patients. In addition, the combination of viteiximab and tripril mab worked quickly, and a treatment response was observed in 88.2% of patients at the first evaluation (8 1 weeks).

Vidicon monoclonal antibody (RC48-ADC), an antibody-coupled drug targeting HER2, was approved in June 2021 for the treatment of advanced gastric cancer positive for HER2 in China. Advanced urothelial cancer approved for first-line treatment progression in January 2022. Its C005 study was a Phase II, open-label, multicenter, single-arm study of patients with locally advanced or mUC HER2(IHC state 3+ or 2+) and included 43 patients who had at least one systemic chemotherapy failure, with an ORR of 51.2%, and a prespecified subgroup should be observed, such as liver metastasis and patients who had been treated with PD-1/PD-L1 in the past. The median PFS and OS were 6.9 months (95%CI, 5.6–8.9) and 13.9 months (95% CI, 9.1–NE), respectively, with good safety and no Grade 4 or 5 TRAE.

As the fifth listed domestic PD-1 drug, Paxil Ampley monoclonal antibody injection has obvious differentiation advantages, and is the only new PD-1 monoclonal antibody adopting IgG1 subtype and modifying Fc segment in the world, which can avoid the problems of self-aggregation of IgG4 subtype PD-1 monoclonal antibody and binding to in vivo anti-tumor IgG1; At the same time, the IgG1 subtype is easy to be purified, which can reduce host cell residue and the occurrence of fever and infusion reaction. The Ampley monoclonal antibody utilizes genetic engineering technology to carry out amino acid mutation in the Fc segment of the heavy chain to form FC silencing, thereby remarkably reducing effector T cell depletion. On the other hand, Fc-segment modification also reduced ADCR effect, reduced IL-8 release, enhanced curative effect, and reduced IL-6 release, thereby reducing irAE, and significantly improving the clinical safety of Ampley monoclonal antibody. Crystal structure analysis showed that Ampley mab had unique PD-1 binding epitope, which dissociated more slowly with PD-1 and permanently blocked PD-1/PD-L1 binding. Different from other PD-1 products already on the market, it is possible that the efficacy and safety of Ampley monoclonal antibody are better.

In this study, we intended to add immunotherapy to the treatment of patients with locally advanced urothelial carcinoma of the bladder who were intolerant to locally advanced cisplatin, so as to obtain the efficacy and safety indicators for the platinum-intolerant patients with locally advanced urothelial carcinoma of the bladder treated with the neoadjuvant therapy of vidicon combined with Ampley monoclonal antibody, and to provide guidance for the follow-up Phase III clinical trial and clinical application.

III. Study purpose and endpoint

1. Research purposes

1.1 Main research objectives:

To evaluate the pathological complete response rate (pCR rate) after radical cystectomy in patients with HER2 expression, cisplatin-intolerant cT2-T4aNxM0 vesical urothelial carcinoma treated with neoadjuvant therapy of vidicon combined with Ampley monoclonal antibody.

1.2 Secondary study objectives:

A) Evaluating the pathological descending rate;

B) Evaluating event-free survival (EFS);

C) Evaluating overall survival (OS);

D) To evaluate the safety of the new adjuvant therapy and its impact on radical cystectomy (evaluated according to NCI-CTCAE v5 and surgical complications according to Clavien-Dindo scoring criteria).

2. Analysis set:

2.1 Safety analysis set: Includes all patients who received at least 1 dose of any study drug (any component of neoadjuvant combination therapy).

2.2 Effectiveness analysis set: Includes all patients who received at least 1 dose of any study drug treatment (any component of neoadjuvant combination therapy) and had a radical cystectomy following that treatment.

3. Observation indicators

3.1 Main indicators:

Pathological complete response rate (pCR rate): the pathological stage after radical cystectomy was pT0N0 (based on effectiveness analysis)

3.2 Secondary indicators:

A) Pathological decline rate: the proportion of patients with pathological stage \leq pT1N0 (based on the efficacy analysis set) after radical cystectomy;

B) Safety: to evaluate the safety and impact on radical cystectomy of the new adjuvant therapy (evaluated according to NCI-CTCAE v5 and surgical complications according to Clavien-Dindo scoring criteria) (based on the safety analysis set);

C) Event-free survival (EFS): EFS is defined as the time from enrollment to disease progression, death from any cause, or new onset of another tumor.

D) Total survival (OS): Total survival was defined as the time from enrollment to death for any cause.

IV. Study population

1. Subjects

Patients diagnosed with bladder urothelial carcinoma of cT2-T4aNxM0 expressing HER2

through TURBT, cystoscopy biopsy and imaging evaluation were screened according to the entry and exit criteria.

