J. AEs and laboratory abnormalities will be graded according to NCI-CT Cae Version 5.0 (drugs), and CLAVIEN-DINDO (surgery), and all AEs will be evaluated for severity. Only SAEs should be reported after informed consent has been signed but prior to initiation of study drug administration. After initiation of study drug, all AEs and SAEs, regardless of relationship of study drug and procedure, will be evaluated and documented until 28 days after the last dose (including chemotherapy) or initiation of new anticancer therapy (whichever occurs first). Assessment and documentation of surgery-related adverse events should be performed within 90 days after surgery.

K. VDT will be administered intravenously every 3 weeks. The infusion time for the first infusion (Cycle 1, Day 1) should be not less than 60 minutes; If well tolerated, subsequent infusions should take no less than 30 minutes, the shortest time allowed for an infusion. Patients must be monitored for at least 60 minutes in an area equipped with resuscitation equipment and emergency medications following the infusion of vidicon on the first day of Cycles 1 and 2. Beginning with cycle 3, a minimum of 30 minutes of monitoring is required in areas equipped with resuscitation equipment and emergency medications. VID should not be coadministered with any other drugs. At each cycle, vidicon will be administered prior to PD-1 drug administration.

L. PyAmpley monoclonal antibody will be administered intravenously every 3 weeks. Administration of the drug was on the same day as that of the vidicon.

M. After radical surgery, the pathological staging after neoadjuvant therapy will be evaluated by the investigator based on the pathological results of surgical samples.

N. During the screening stage, patients must provide tumor tissue samples of TURBT and relevant pathological report at the same time, and can choose to send fresh surgical tissue or pathological white sheet for biomarker analysis. Fresh tumor samples also need to be collected during radical surgery. Patients with disease progression will be asked if an optional biopsy has been performed (see central laboratory sample management manual).

O. Patients were required to complete the EQ-5D-5L and EORTC QLQ-C30 questionnaires (Appendix 11, 12). Where feasible, patients are required to complete questionnaires prior to administration of study drug or any other procedure.

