Safety was evaluated by monitoring and documentation of all adverse events classified by NCI-CTCAE v5.0 or Clavien-Dindo. Laboratory values (eg, hematology, clinical biochemistry, urinalysis), vital signs, ECGs, and physical examinations will also be considered in evaluating safety. All safety data in the safety analysis set will be analyzed using descriptive statistics.

The safety analysis set was defined to include all patients who received ≥ 1 dose of neoadjuvant therapy from the study protocol. EFS rate, OS rate, and adverse events of drug exposure (including duration and dose) will be summarized by safety analysis set population. Adverse events will be described coded according to the Medical Dictionary for Regulatory Activities (MedDRA) terms and graded according to NCI-CTCAE v5.0 or Clavien-Dindo.

Adverse events in 5.4.4.1

AE reporting terms (investigator description in eCRF) will be coded using the International Dictionary of Medical Terms (MedDRA). AEs were coded according to low-level terms, preferred terms, and major system organ class in MedDRA (version 20.0 or higher).

Vi. research interventions *

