8.1.4 Reporting of adverse events

Collection, reporting and handling of aes in 8.1.4.1

All AEs related to the protocol-specified procedures that occurred after the informed consent form was signed and prior to administration of the test article were recorded on the CRF.

Records of AEs should include a description of the AE and all associated symptoms, when it occurred, severity, duration, association with test article, action taken, and final outcome and outcome. The recording of AEs must use medical terminology, and if subject symptoms and signs can be summarized by a common etiology, the diagnosis should be recorded as much as possible. In addition to the indicators related to disease progression, all clinical events and clinically significant laboratory adverse reactions could be handled with reference to the Evaluation Standard for Common Adverse Reaction Events (CT cae) version 5.0; Post-surgical AEs were only evaluated by Clavien-Dindo classification. Treatment-emergent adverse reactions will be documented by the investigator.

Collection and reporting of SAEs in 8.1.4.2

All SAEs, regardless of cause or drug-related, that occurred between the time the subject signed the informed consent form and 4 weeks after completion of study dosing were reported using the SAE Reporting Form. In the event of SAE, the investigator shall immediately take appropriate treatment measures for the subject to ensure the safety of the subject, and report to the drug registration applicant, National Medical Products Administration, the Provincial Food and Drug Administration, the ethics committees of the corresponding clinical trial centers, and the Medical Department of Health and Sanitation Committee, Medical Administration and Hospital Authority within 24 hours and to the ethics committee of the team leader unit in a timely manner. The initial report should, to the extent possible, include the following: source of report, test article name, serious adverse events name, time of occurrence, severity, duration, relevance to the test article, action taken, and outcome.

IX. Data collection and management

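### Clavien-Dindo surgical complications are assigned to all dosed patients rather than operated patients, and no listed indicator counts failure to reach cystectomy

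*Protocol*

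**What the plan says.** **Objective.** Section III, 1.2 D is "To evaluate the safety of the new adjuvant therapy and its impact on radical cystectomy".

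**Indicator and set.** Section III, 3.2 B names NCI-CTCAE v5 and "surgical complications according to Clavien-Dindo scoring criteria) (based on the safety analysis set". Section III, 2.1 defines that set: "Safety analysis set: Includes all patients who received at least 1 dose of any study drug". Section 5.4.4 adds: "All safety data in the safety analysis set will be analyzed using descriptive statistics".

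**Operated set.** Section III, 2.2 defines the patients who were dosed and "had a radical cystectomy following that treatment". The protocol uses this set for pCR and pathological downstaging, and for a second analysis of overall survival.

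**Collection of surgical events.** Section 8.1.4 states: "Post-surgical AEs were only evaluated by Clavien-Dindo classification". Note J to the visit schedule states: "Assessment and documentation of surgery-related adverse events should be performed within 90 days after surgery".

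**Unoperated patients are foreseen.** The exit criteria (Section IV, 1.3) and 5.2.4 both describe patients who start treatment and do not have surgery. The background (2.1) says of checkpoint inhibitors that "some patients lose the opportunity of radical surgery due to adverse events caused by ICIs treatment".

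**The concern.** A surgical complication can occur only in someone who has had surgery. If the rate is taken over all dosed patients, each patient who loses the operation adds to the denominator and can add nothing to the numerator. The result then moves the wrong way: a regimen that costs more patients their cystectomy shows a lower surgical complication rate.

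The lost operation is also not an outcome in its own right. The trial is meant to guide a Phase III study in cisplatin-intolerant patients. For that purpose, how many treated patients still reach planned surgery is a central part of the impact on cystectomy.

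**Working it through.** **Inputs from the protocol (5.4.1).** 43 evaluable patients, 10% dropout, 48 recruited. The protocol's own figure reproduces: 43 / (1 − 0.10) = 47.8, rounded up to 48.

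**Inputs that are assumptions.** The protocol states no surgical complication rate and no proportion reaching surgery. I take 48 dosed. In the central case the whole 10% allowance is dosed but unoperated, leaving 43 operated. The cases with 46 and 38 operated, and every count of complications, are also assumed, to show a range.

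**Effect of the denominator.** Rate per dosed = (rate per operated) × (operated / dosed). In the central case the factor is 43/48 = 0.896.

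| Operated of 48 | Patients with a complication | Per operated | Per dosed | Understatement |
|---|---|---|---|---|
| 46 | 14 | 30.4% | 29.2% | 1.3 points |
| 43 | 13 | 30.2% | 27.1% | 3.1 points |
| 43 | 20 | 46.5% | 41.7% | 4.8 points |
| 43 | 26 | 60.5% | 54.2% | 6.3 points |
| 38 | 11 | 28.9% | 22.9% | 6.0 points |
| 38 | 23 | 60.5% | 47.9% | 12.6 points |

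**Direction.** Hold the risk among operated patients at 46.5% and reduce the number operated from 43 to 38. The expected number with a complication is 0.465 × 38 = 17.7, and the rate per dosed is 17.7/48 = 36.8%. The reported figure falls from 41.7% to 36.8% although surgery has become no safer.

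**Is lost surgery counted elsewhere?** Each listed indicator in turn:
- pCR and downstaging use operated patients only, so a patient who loses surgery leaves both.
- EFS events (Section III, 3.2 C and 5.4.3.2) are progression, death or a new tumour. Becoming unfit for surgery through toxicity is none of these.
- OS counts deaths only.
- CTCAE grades the toxicity, not the cancelled operation.

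**What the missing summary would show.** With exact (Clopper-Pearson) 95% intervals, 5 of 48 without cystectomy is 10.4% (3.5% to 22.7%), and 10 of 48 is 20.8% (10.5% to 35.0%). Both counts are assumed.

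**The case against.** **The protocol does not write out a rate.** Indicator B gives no numerator or denominator, and 5.4.4 promises only descriptive statistics. Surgical events are collected only after surgery, so an analyst might divide by operated patients anyway, and table denominators are often settled in the SAP. This stands in part: the diluted percentage follows from applying the stated set and is not printed in the protocol. But the protocol does name a set for this indicator, so a SAP that used operated patients would be departing from it.

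**Clavien-Dindo is not the only measure.** A reader might infer that the whole objective rests on it. The documents do not support that: CTCAE v5 is named in the same indicator and would capture a toxicity that leads to cancellation. Clavien-Dindo alone applies to post-surgical events.

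**Lost surgery is not invisible.** A reader might also infer that the trial could not answer objective D. That is too strong. The sizes of the two analysis sets would broadly show how many dosed patients were not operated, the main reason for stopping treatment goes on the eCRF (Section IV, 1.3), and EFS on the safety set counts progression or death in these patients. What is missing is a named summary; much of the information is there.

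**The size is small.** In the central case the shift is 4.8 points. The approximate 95% sampling error of 20/43 is 1.96 × √(0.465 × 0.535 / 43), about ±15 points. The indicator is secondary and descriptive, and no decision depends on it. This stands. It limits the weight of the dilution but leaves the missing outcome untouched.

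**Conclusion.** The concern holds in two parts.

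1. The safety set is the wrong denominator for events that can follow only from surgery. Applied as written, it understates the complication rate by the factor operated/dosed. That is about 3 to 6 points at 43 of 48 operated, for assumed complication rates of roughly 30% to 60%. This rests on reading the stated set as the denominator and on assumed surgery and complication rates, so the size is illustrative and modest.
2. No listed indicator counts failure to reach cystectomy, although objective D is about impact on cystectomy and the background names this harm. This part rests on the text alone and is the weightier one.

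Delayed surgery is a related gap, but it cannot yet be defined. The visit schedule places surgery 28 to 42 days after the last dose, while 6.1 places it 4 weeks after neoadjuvant treatment. Those passages must be reconciled before any operation can be classed as late.

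**What to change.** In Section III, 3.2 B and in 5.4.4:
- Keep CTCAE drug adverse events on the safety analysis set.
- Summarise Clavien-Dindo complications among patients who had cystectomy, using the set already defined in Section III, 2.2.
- Report, over all dosed patients and with an exact 95% confidence interval, the proportion not undergoing cystectomy, broken down by recorded reason.
- Add a proportion with delayed surgery only once the timing in the visit schedule and in 6.1 has been reconciled.

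**Cost.** Mostly wording. The eCRF records why study treatment was stopped. It may need one further field for patients who complete treatment and are then not operated, because the reason for stopping treatment does not cover them. The reported complication rate will be higher, and so less favourable, whenever some dosed patients are not operated.
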